Unfortunately, there is currently no specific defined treatment to prevent or reverse muscle weakness in mechanically ventilated patients. Some recent work suggests that vigorous physical therapy, involving cycling exercise of ICU patient, may improve outcomes (3). Such treatments are labor intensive, however, and few ICU's currently have the manpower or equipment to provide such treatments. In addition, many MICU patients require significant sedation and are too obtunded to realistically participate in any active exercise training regimen. In the University of Kentucky MICU patients are supposed to receive 3 treatments of passive range of motion by physical therapists a week, but compliance with this regimen is poor and only a small minority of patients receive even this modest level of therapy. This minimal level of physical exercise for bed bound ICU patients is typical for patients across the country, with the result that many patients who walk into hospitals need to leave in wheel chairs. Depending upon their health insurance status, some of these patients receive outpatient rehabilitation, but many receive little or no therapy even after hospital discharge.

Recently, a number of companies have developed electrical stimulation devices that can exercise the quadriceps, the major leg muscle, by stimulating this muscle to rhythmically contract. This newer technology represents an advance over older electrical stimulators which can be extremely painful and produce potentially injurious robot-like muscle contractions. Currently this technique is being used to provide rehabilitation to leg muscles after knee surgery in orthopedic patients. The purpose of the present study is to use one of these newer stimulators, the All-Stim 2, in mechanically ventilated MICU patients to provide a means of safely, nonvolitionally exercising the leg muscles of these patients. We postulate that this form of treatment will increase leg muscle strength in these patients, reduce the duration of hospitalization, improve long term mobility, and reduce indices of long term disability.

**Objectives:** List your research objectives. You may reference grant application/sponsor's relevant protocol pages and attach as an appendix in the E-IRB "Additional Information" section, however, a summary paragraph must be provided in the text box below.

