The objective for this study is to determine if daily exercise using All-Stim 2 stimulation of quadriceps muscles will increase leg strength and improve outcomes (duration of hospitalization, long term mobility, long term disability) for mechanically ventilated MICU patients. We plan to randomize patients accepted into this protocol to administration of either sham exercise (i.e. placement of All-Stim 2 units on the legs for 30 minutes a day without activation of the electrical stimulation program) or active exercise (placement of All-Stim 2 electrodes on both legs and stimulating quadriceps muscles to rhythmically contract for 30 minutes a day). The two groups (sham and active exercise) will be treated for 30 minutes a day for seven days. The effects of exercise on quadriceps strength will be assessed by measuring quadriceps force generation (QuadTw) in response to magnetic stimulation of the femoral nerves. The QuadTw assessment will be made immediately before institution of sham or active exercise and will be repeated one day after the conclusion of the seven day training regimen. Chart review and patient follow-up will be used to determine if this treatment regimen has an impact on clinical outcome measures, i.e. duration of hospitalization, long term mobility, long term disability.

**Study Design:** Describe the study design (e.g., single/double blind, parallel, crossover, etc.). Indicate whether or not the subjects will receive placebo medication at some point in the research procedures. Also, indicate whether or not the subjects will be randomized in this study. You may reference sponsor's protocol pages and attach as an appendix in the E-IRB "Additional Information" section, however, a summary paragraph must be provided in the text box below. (Including the study design table from a sponsor's protocol is helpful to IRB members.)

*Community-Based Participatory Research:* If you are conducting [community-based participatory research \(CBPR\)](#), describe strategies for involvement of community members in the design and implementation of the study, and dissemination of results from the study.

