*Research Repositories:* If the purpose of this submission is to establish a Research Repository (bank, registry) indicate whether the material you plan to collect would or would not be available from a commercial supplier, clinical lab, or established IRB approved research repository. Provide scientific justification for establishment of an additional repository collecting duplicate material. Describe the repository design and operating procedures. For relevant information to include, see the UK Research Biospecimen Bank Guidance [\[PDF\]](#) or the UK Research Registry Guidance [\[PDF\]](#)

The basic study design is to:

- (a) obtain informed consent;
- (b) measure magnetic stimulated quadriceps twitch (QuadTw) strength bilaterally;
- (c) randomize patients to treatment with either:

Sham therapy, consisting of bilateral placement of All-Stim 2 electrodes for 30 minutes a day without activation of the electrical circuitry of the unit, or

Active therapy, using the All-Stim 2 electrodes to actively produce a rhythmic quadriceps contraction for 30 minutes a day.

We plan to have a total of 24 patients in the study, with two patients randomized to active treatment for every one patient given sham treatment. As a result we anticipate the final group studied will include 14-16 active treatment patients and 6-8 sham treatment patients.

- (d) continue these regimens daily for 7 days;
- (e) remeasure magnetic stimulated QuadTw on day 8;
- (f) the research team will visit the patient until discharge and will record duration of mechanical ventilation, duration of ICU stay, and total duration of hospitalization; and,
- (g) patients will be visited by a member of the research team at 28 days after study entry to assess the distance that can be walked in 6 minutes (i.e. the 6 minute walk test) and to assess patient well being using the St. Georges Research Questionnaire (SGRQ, a commonly used and extensively validated instrument to assess patient well being).

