**Hospital Outcomes:** After recruitment into studies, electronic hospital records will be reviewed twice a week to determine the time from the point of initial study measurements to successful weaning from mechanical ventilation (defined as remaining off all mechanical ventilation for more than 4 days). Alternative outcomes that will be recorded, for patients that are not weaned from mechanical ventilation, include transfer to a chronic facility for long term weaning from mechanical ventilation (i.e. an LTAC) or death. Deaths will be further subclassified as death due to withdrawal of care and death due to progression of disease. We will also record total ICU stay, total days of hospital stay, and incidence of recurrent respiratory failure, defined as a requirement for reintubation either during the initial hospitalization or at any time out to day 28 after entry into the study. We will also record hospital readmission rates.

**Follow-up Visit (28 days).** At follow-up visits we will assess the distance walked in 6 minutes and we will ask patients if they have returned to work (either full time or part time). We will also have patients fill out the St. Georges respiratory questionnaire (SGRQ) on return visits. This questionnaire evaluates patient's perceptions about their respiratory health, including their assessment of the ability to perform simple tasks of daily living. The PI and/or [name] will visit the patient's domicile (or other site of habitation) to obtain these assessments.

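### Reintubation is counted to the later of discharge and day 28, so stays beyond day 28 give the longer-staying arm more time to record events

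*Combined protocol and SAP*

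**What the plan says.** The Hospital Outcomes paragraph of Research Procedures lists recurrent respiratory failure among the items to be recorded, "defined as a requirement for reintubation either during the initial hospitalization or at any time out to day 28 after entry into the study". It then adds: "We will also record hospital readmission rates". No window or denominator is given for readmission.

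On collection, the same paragraph says that "electronic hospital records will be reviewed twice a week", without saying when the review stops. Study Design, item (f), says that "the research team will visit the patient until discharge", and item (g) adds one visit at 28 days after entry. The Follow-up Visit paragraph lists walking distance, return to work and the SGRQ for that visit. It does not mention reintubation or readmission.

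Length of stay is itself something the treatment is meant to change. Background states: "We postulate that this form of treatment will increase leg muscle strength in these patients, reduce the duration of hospitalization". Objectives names it again among the results that treatment should improve: "improve outcomes (duration of hospitalization, long term mobility, long term disability".

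The Statistical Analysis Plan names t tests before and after therapy with a Tukey post-hoc test at 0.05. It gives no method for an incidence, no common observation window, and no rule for deaths or for transfers to a long-term facility. On size, Study Design says: "We plan to have a total of 24 patients in the study", allocated two to one.

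**The concern.** The two limbs of the definition are joined by an either/or. A patient discharged on day 15 is counted to day 28, and a patient in hospital until day 60 is counted to day 60. Observation time for one outcome then depends on another outcome, length of stay, which the protocol expects to differ between arms.

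If treatment does shorten stays, and some stays run past day 28, the active arm has less time in which a reintubation can be recorded. It would show fewer events with no change in the underlying risk. The error would point the way the investigators hope, and nothing in the analysis plan would correct it.

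**Working it through.** The documents state no reintubation rate, length of stay or power calculation for this outcome, so there is no figure of the plan's own to reproduce. The check asks what the definition records when treatment has no effect on reintubation.

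**From the documents:** window = the later of discharge and day 28 (Hospital Outcomes, plain reading); 24 patients at 2:1, so 16 active and 8 sham (Study Design).

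**Assumed:** the same constant daily hazard in both arms, set by a 28-day risk p of 20% (10% and 30% also tried); stays counted from entry; death and time on the ventilator ignored.

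**Step 1, fixed stays.** Hazard h = −ln(1 − p)/28 = −ln(0.8)/28 = 0.00797 per day. Recorded rate for a stay of L days = 1 − exp(−h × max(28, L)) = 1 − 0.8^(max(28, L)/28).

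- 20 vs 14 days: 20.0% vs 20.0%. Both windows are 28 days, so there is no bias.
- 42 vs 30 days: 1 − 0.8^1.5 = 28.5% vs 1 − 0.8^(30/28) = 21.3%.
- 56 vs 35 days: 1 − 0.8^2 = 36.0% vs 1 − 0.8^1.25 = 24.3%.

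Only days in hospital after day 28 produce a difference.

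**Step 2, stays that vary between patients.** For exponential stays with mean m, the recorded rate is 1 − 0.8 × [1 − exp(−28/m) × hm/(1 + hm)]. For m = 30.4: exp(−28/30.4) = 0.398, hm = 0.242, hm/(1 + hm) = 0.195, giving 1 − 0.8 × (1 − 0.0776) = 26.2%.

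| Mean stay, sham vs active (days) | Share beyond day 28 | Recorded rate | False difference |
|---|---|---|---|
| 10 vs 7 | 6% vs 2% | 20.4% vs 20.1% | 0.3 points |
| 20 vs 15 | 25% vs 15% | 22.7% vs 21.3% | 1.4 points |
| 30.4 vs 22.8 | 40% vs 29% | 26.2% vs 23.6% | 2.6 points |
| 40 vs 30 | 50% vs 39% | 29.6% vs 26.1% | 3.5 points |
| 30.4 vs 15.2 | 40% vs 16% | 26.2% vs 21.4% | 4.8 points |

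For 30.4 vs 22.8 days the gap is 1.6 points at p = 10% and 3.2 points at p = 30%. Lognormal stays (log-SD 0.7, medians 21 vs 16) at p = 20% give 23.7% vs 21.9%, or 1.8 points.

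**Step 3, are stays past day 28 plausible?** Background estimates 50,000 ventilated patients at any time and 600,000 per year, which implies 50,000/600,000 × 365.25 = 30.4 days of ventilation on average. If durations were exponential, exp(−28/30.4) gives about 40% beyond 28 days. This is a national estimate of ventilation time, not trial data on stay after entry. It shows only that such stays cannot be ruled out.

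**Step 4, random error.** Standard error of a difference at 20% = √[0.2 × 0.8 × (1/16 + 1/8)] = √0.03 = 17 points. At the lower group sizes that Study Design anticipates (14 and 6), it is √[0.16 × (1/14 + 1/6)] = 20 points.

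**Step 5, the same case with a fixed window.** Counting to day 28 for everyone gives 20% in both arms whatever the stays, provided events after discharge are captured equally. Unequal capture would reopen the problem even for short stays. If post-discharge events were missed altogether, stays of 20 vs 14 days would record 1 − 0.8^(20/28) = 14.7% vs 1 − 0.8^(14/28) = 10.6%.

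**The case against.** **The sentence may mean something narrower.** It could be read as events in hospital or after discharge, all up to day 28, and the planned contact is at 28 days. That reading leaves the hospitalisation limb with nothing to add, so the plain reading is the better one. Nothing in the documents settles it, and a clarifying phrase is needed on either reading.

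**The hazard model is crude.** A reintubation requires an earlier extubation, so a patient still ventilated on day 40 has not been at risk for 40 days. Reintubation can also lengthen the stay. This stands as a limit on the sizes above, which are illustrations. It does not remove the dependence of the window on the discharge date.

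**A fixed window also leaves unequal time since extubation.** That is true: at an assumed 1% per day, extubation on day 7 vs day 14 gives 1 − exp(−0.21) = 18.9% vs 1 − exp(−0.14) = 13.1% by day 28. But following every randomised patient for the same time from entry is the standard randomised comparison. Earlier extubation is then part of what treatment does, whereas extra counting days from a late discharge come only from the definition.

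**The outcome hardly matters here.** It is not in Objectives or the Study Design list and has no planned test, and random error dwarfs the artefact. This stands and sets the severity.

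**Stronger readings.** A reader might infer a false gain of 4 to 9 points by supposing that everyone stays 35 or 45 days. At 0.5%, 1% and 2% per day, 1 − exp(−hL) does give 16.1% vs 20.1%, 29.5% vs 36.2% and 50.3% vs 59.3%. The documents do not support having every patient in hospital past day 28.

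A reader might also infer an opposite bias in readmission: at 1% per day to day 28, discharge on day 14 vs day 21 gives 13.1% vs 6.8%. The plan states no readmission window, so this is missing detail and not an error. Those stays would also leave no reintubation artefact, so the two calculations cannot describe the same patients.

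**Conclusion.** The point holds, with a condition, and is minor. On its plain reading the definition lets observation time depend on the discharge date. It favours the arm with shorter stays only to the extent that stays exceed day 28 after entry.

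With a 20% risk by day 28, equal hazards and varying stays, the artefact is about 1 to 5 points. It approaches zero when few patients stay that long and is larger only if nearly all do. It is well inside random error with 24 patients and could not reasonably drive a conclusion alone. It is still a directional flaw in the definition, and it costs little to remove. The stays and risks behind these sizes are assumptions, because the documents supply neither.

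**What to change.** In Hospital Outcomes, define recurrent respiratory failure as reintubation by day 28 after entry for every randomised patient, whether in hospital, transferred or discharged. Report deaths by day 28 beside it as a competing event, and list in-hospital reintubations after day 28 separately.

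Add a dated question about reintubation at any hospital to the existing day-28 visit, so that capture after discharge is the same in both arms. Potential Risks places the walk test 28 days after discharge, whereas Study Design places it 28 days after entry. The two should be reconciled, and the dated question lets the count stop at day 28 after entry in either case.

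In the same edit, give readmission a window and a denominator, for example days alive and out of hospital up to day 28. The question about admissions elsewhere would serve this too.

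The cost is two definition sentences, one visit question and an IRB modification. A few late in-hospital events leave the main count. Subject Info To-Date shows 15 of 24 patients already enrolled. For them, events at other hospitals would have to be sought retrospectively or reported as not ascertained. The change should be dated and made before reintubation is compared between arms.

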#### Attachments

**Data Collection:** List the data or attach a list of the data to be collected about or from each subject (e.g. interview script, survey tool, data collection form for existing data).

If the research includes survey or interview procedures, the questionnaire, interview questions or assessment scales should be included in the application (use attachment button below).

The data collection instrument(s) can be submitted with your application in draft form with the understanding that the final copy will be submitted to the IRB for approval prior to use (submit final version to the IRB for review as a modification request if initial IRB approval was issued while the data collection instrument was in draft form).

**Note:** The IRB approval process does not include a statistical review. Investigators are strongly encouraged to develop data management and analysis plans in consult with a statistician.

See above section which includes all this information.

#### Attachments

**Resources:** Describe what resources/facilities are available to perform the research (i.e., staff, space, equipment). Such resources may include a) staffing and personnel, in terms of availability, number, expertise, and experience; b) psychological, social, or medical services, including counseling or social support services that may be required because of research participation; c) psychological, social, or medical monitoring, ancillary care, equipment needed to protect subjects; d) resources for subject communication, such as language translation services, and e) computer or other technological resources, mobile or otherwise, required or created during the conduct of the research. Please note: Some mobile apps may be considered mobile medical devices under FDA regulations (see [FDA Guidance](#)). Proximity or availability of other resources should also be taken into consideration, for example, the proximity of an emergency facility for care of subject injury, or availability of psychological support after participation.

Research activities conducted at performance sites that are not owned or operated by the University of Kentucky, at sites that are geographically separate from UK, or at sites that do not fall under the UK IRB's authority, are subject to special procedures for coordination of research review. Additional information is required (see [IRB Application Instructions - Off-Site Research](#) web page); supportive documentation can be attached in the E-IRB "Additional Information" section. Provide a written description of the role of the non-UK site(s) or non-UK personnel who will be participating in your research. The other site may need to complete its own IRB review, or a cooperative review arrangement may need to be established. Contact the Office of Research Integrity at [contact] if you have questions about the participation of non-UK sites/personnel.

If the University of Kentucky is the lead site in a multi-site study, or the UK investigator is the lead investigator, describe the plan for managing the reporting of unanticipated problems, noncompliance and submission of protocol modifications and interim results from

the non-UK sites.

The PI has studied various aspects of respiratory muscle function and dysfunction over a 25 year period. During this time, the PI has published approximately 100 peer reviewed papers on original research related to respiratory muscle and other critical care topics, as well as 150 abstract presentations at national meetings.

The PI is currently funded by an NIH grant as PI and also receives support as a co-investigator from another NIH grant held by [name]. The PI's laboratory is equipped with a cart containing all the apparatus required to obtain QuadTw measurements. Specifically, the cart is equipped with two MagStim 200 magnetic stimulators equipped with dual figure of eight coils for nerve stimulation, the quad board used for positioning the leg, and a force transducer with a computer interface. This cart is mobile and can be moved to the ICU rooms when needed to assess leg strength. The cart is equipped with sterile wipes that will be used to disinfect all exposed surfaces before and after entrance and exit from patient rooms. Both the Magstim and All Stim 2 units are FDA approved and are in common usage in the USA and other countries for assessment of neurological function and quadriceps conditioning, respectively.

**Potential Risks:** Describe any potential risks or likely adverse effects of the drugs, biologics, devices or procedures subjects may encounter while in the study. Please describe any physical, psychological, social, legal or other risks and assess their likelihood and seriousness.

Use of magnetic twitch stimulation for femoral nerve stimulation is essentially painless. Use of the All-Stim 2 device produces a mild tingling sensation but is also essentially painless at the settings we will use. Removal of the All-Stim 2 electrodes, which have sticky adhesives on their inner surface, could theoretically cause pain in a very hairy individual (this will be dealt with as described below). Both devices could theoretically produce problems in individuals with pacemakers or implanted defibrillators, so patients with these devices will be excluded from the study. We will ask patients to perform a six minute walk test at 28 days after discharge and use a pedometer to assess distance walked. This test has been previously used to assess patient outcomes after ICU discharge (see references 1, 2) with no reported complications. There is essentially no risk to performance of chart reviews or evaluation using the SGRQ.

[Back to Top](#)

**Safety Precautions:** Describe the procedures for protecting against or minimizing any potential risks, *including risks of breach of confidentiality or invasion of privacy*. Where appropriate, discuss provisions for ensuring necessary medical or professional intervention in the event of adverse events, or unanticipated problems involving subjects. Also, where appropriate, describe the provisions for monitoring the data collected to ensure the safety of subjects. If vulnerable populations other than adults with impaired consent capacity are to be recruited, describe additional safeguards for protecting the subjects' rights and welfare.

Extremely unstable patients, i.e. patients requiring high levels of PEEP, high levels of oxygen or in severe shock, will be excluded from study.

There are no reported adverse effects using magnetic stimulation to assess peripheral nerves except for an isolated report of interference with pacemaker function in one patient. For this reason, we will exclude patients with pacemakers from this study.

There is no risk to the patient for chart review assessment.

There have no reports of previous injury with use of the All Stim 2 device. Application of the All Stim 2 device will require placement of sticky pads on the anterior thighs so, as a result, removal of the device could cause some pain if the sticky pads pull on the thighs of an excessively hairy individual. For this reason, if a patient has significant thigh hair we will warn them of this risk and offer to remove the thigh hair (i.e. by shaving or use of Nair) prior to use of the device. Both the PI and [name] have used the device without incident; we would not expect the average patient to be so hairy that this should represent a serious concern.

**Benefit vs. Risk:** Describe potential benefits to the subject(s); include potential benefits to society and/or general knowledge to be gained. Describe why the risks to subjects are reasonable in relation to the anticipated benefit(s) to subjects and in relation to the importance of the knowledge that may reasonably be expected to result. If you are using vulnerable subjects (e.g., impaired consent capacity, pregnant women, etc...), justify their inclusion by describing the potential benefits of the research in comparison to the subjects' vulnerability and the risks to them. For information about inclusion of certain vulnerable populations, see the IRB/ORI Standard Operating Procedure for Protection of Vulnerable Subjects [C3.0100] [\[PDF\]](#).

The sensation associated with magnetic stimulation is not painful but is associated with a sudden involuntary contraction of the muscles being stimulated distal to the nerve. The use of the All Stim 2 device produces a tingling sensation.

We do not believe these techniques pose a significant risk to patients, in that no long term adverse consequences should occur providing the exclusion criteria used for this study are rigorously followed.

There are, however, important potential benefits for the patients taking part in this study. Use of this rehabilitation technique may well increase leg strength, improve ambulation, facilitate early mobilization, shorten ICU and hospital stays, improve long term mobility, and increase the long term ability of patients to perform activities of daily living.

**Available Alternative Treatment(s):** Describe alternative treatments and procedures that might be advantageous to the subjects, should they choose not to participate in the study. This should include a discussion of the current standard of care treatment(s).

Currently these patients receive only minimal levels of passive range of motion in the ICU to try to maintain leg muscle function. There

is no alternative exercise regimen that is currently being employed routinely in the MICU at the University of Kentucky.

[Back to Top](#)

**Research Materials, Records and Privacy:** Identify the sources of research material obtained from living human subjects. Indicate what information (specimens, records, data, genetic information, etc.) will be recorded and whether use will be made of existing specimens, records or data. Explain why this information is needed to conduct the study.

*Return of Research Results or Incidental Findings (if applicable):*

If research has the potential to identify individual results or discover incidental findings that could affect the health of a subject, describe plans to assess, manage, and if applicable disclose findings with individual subjects or provide justification for not disclosing. For IRB expectations, refer to the UK IRB "Frequently Asked Questions (FAQs) on the Return of Research Results or Incidental Research Findings" [[PDF](#)].

All data collected from the study (i.e. tracings of force measurements, demographic/clinical data obtained from chart review,) will be placed in a folder which will be stored in a locked filing cabinet in the office of the principal investigator in MN616. None of this information will be shared with other investigators. All folders will be given a study number and further analysis of mean data obtained from patient study folders will be carried out with only the patient study number as identification. Folders containing mean data will also be stored in the locked filing cabinet in MN616.

**Confidentiality:** Specify where the data and/or specimens will be stored and how the researcher will ensure the privacy and confidentiality of both. Please address the following items or indicate if the following has been addressed in a HIPAA or Limited Review form:

- physical security measures (e.g., locked facility, limited access);
- data security (e.g., password-protection, data encryption);
- who will have access to the data/specimens and identifiers;
- safeguards to protect identifiable research information (e.g., coding, links, certificate of confidentiality);
- procedures employed when sharing material or data, (e.g., honest broker if applicable, written agreement with recipient not to re-identify, measures to ensure that subject identifiers are not shared with recipients).
- management after the study

Describe whether data/specimens will be maintained indefinitely or destroyed. If maintained, specify whether identifiers will be removed from the maintained information/material. If identifiers will not be removed, provide justification for retaining them. If the data/specimens will be destroyed, describe how and when the data/specimens will be destroyed. For multi-site studies, the PI consults the study sponsor regarding retention requirements, but must maintain records for a minimum of six years after study closure. Also, specify who will access the identified data/specimens, and why they need access. If applicable, describe what measures will be taken to ensure that subject identifiers are not given to the investigator. If applicable, describe procedures for sharing data/specimens with entities not affiliated with UK.

*HIPAA/FERPA Minimal Access Standards:* The IRB expects researchers to access the minimal amount of identifiers to conduct the study and comply with applicable HIPAA and Family Educational Rights and Privacy Act (FERPA) requirements. If data are going to be collected, transmitted, and/or stored electronically, for appropriate procedures please refer to the guidance document "Confidentiality and Data Security Guidelines for Electronic Data" [[PDF](#)].

*Cloud storage:* For storage of data on cloud services other than UK OneDrive, please verify security settings are sufficient and in accordance with respective departmental, UK Corporate Compliance, and/or UK Information Technology requirements.

*Creation of digital data application/program:* If a research protocol involves the creation and/or use of a computer program or application, mobile or otherwise, please specify whether the program/application is being developed by a commercial software developer or the research team and provide any relevant information regarding the security and encryption standards used, how data is stored and/or transmitted to the research team, what information about the subjects the program/application will collect, etc. For relevant information to include, see Considerations for Protocol Design Concerning Digital Data [[PDF](#)]. The IRB may require software programs created or used for research purposes be examined by a consultant with appropriate Internet technology expertise to ensure subject privacy and data are appropriately protected.

*NIH-funded genomic research:* The National Institutes of Health (NIH) [Genomic Data Sharing \(GDS\) Policy](#) sets forth expectations that ensure the broad and responsible sharing of genomic research data consistent with the informed consent of study participants from which the data was obtained. If you are submitting genomic data to an NIH data repository, describe your NIH data sharing plan.

*Management after study:* Describe how the collected data/specimens will be managed after the end of the study. Specify whether identifiers will be removed from the maintained information/material. If identifiers will not be removed, provide justification for retaining them and specify what steps will be taken to secure the data/specimens (e.g., maintaining a coded list of identifiers separate from the data/specimens).

If the data/specimens will be destroyed, describe how, when, and why this will be done. Note that destruction of primary data may violate [NIH](#) and [NSF](#) retention and sharing requirements, journal publication guidance, and [University Data-Retention policies](#). Additionally, primary data may be necessary for other purposes (to validate reproducibility, for data sharing, or for

evidence in various investigations). PIs should carefully consider whether the destruction of data is justified.

The investigator is responsible for retaining signed consent and assent documents and IRB research records for at least six years after study closure, as outlined in the Study Closure SOP [PDF]. If the research falls under the authority of the FDA or other regulatory agencies, or a study sponsor is involved, additional requirements may apply.

[Back to Top](#)

For publication, no individual identifying features of the patients will be included in abstracts and papers generated using the data collected in this study. As indicated in section 13, all records will be kept in a locked file cabinet in the PI's office. The records for this study will be kept until seven years after the data is published, in keeping with current NIH recommendations on data archiving. The data will be kept in the locked file cabinet in MN616 at least until the data is published and then transferred to a second locked archival filing cabinet in the PI's office. At seven years after publication all data will be destroyed by shredding the documents.

[Back to Top](#)

**Payment:** Describe the incentives (e.g., inducements) being offered to subjects for their time during participation in the research study. If monetary compensation is offered, indicate how much the subjects will be paid and describe the terms and schedule of payment. (It is IRB policy that provision should be made for providing partial payment to subjects who withdraw before the completion of the research. Monetary payments should be prorated or paid in full.)

No subject will be paid for participation in the study

**Costs to Subjects:** Describe any costs for care associated with research (including a breakdown of standard of care procedures versus research procedures), costs of test drugs or devices, and research procedure costs that are the subject's responsibility as a consequence of participating in the research. Describe any offer for reimbursement of costs by the sponsor for research related injury care.

There will be no cost to subjects for participation in the study.

**Data and Safety Monitoring:** The IRB requires review and approval of data and safety monitoring plans for greater than minimal risk research, clinical research, or NIH-funded/FDA-regulated clinical investigations.

If you are conducting greater than minimal risk research, clinical research, or your clinical investigation is NIH-funded/FDA-regulated, describe your Data and Safety Monitoring Plan (DSMP). [Click here for additional guidance on developing a Data and Safety Monitoring Plan.](#)

If this is a *non-sponsored investigator-initiated* protocol considered greater than minimal risk research, clinical research, or your clinical investigation is FDA-regulated, *and* if you are planning on using a Data and Safety Monitoring Board (DSMB) as part of your DSMP, [click here for additional guidance](#) for information to include with your IRB application.

If relying on an independent agent or committee for DSMB services, it is the PI's responsibility to establish the services with the agent or committee. Please be reminded that the PI must submit DSMB reports to the IRB via modification or continuing review. 

To monitor the long term conduct of the study, including monitoring of adverse effects, we will employ a study monitoring board consisting of [name] and [name]. [name] is a well recognized epidemiologist with a background in statistics and his expertise will be used to make the appropriate statistical analysis of the data obtained from these studies. [name] is the Division Chief of Pulmonary/Critical Care Medicine who has had experience in physician compliance with ICU procedures and monitoring of patient safety in the conduct of invasive ICU procedures and he will have responsibility for assessment of safety issues. This board will review the study at twelve month intervals. At these meetings the board will evaluate the quality of the collected data, completeness of data collected for each patient studied, will review the eligibility form to assess compliance with inclusion/exclusion criteria, reporting of adverse effects by patients or nurses, will determine if the study should be continued or terminated because of safety/risk issues, and, at the final meeting, will review the final results.

Adverse effects will be recorded on study forms and reviewed by the DSMB. The DSMB will consider stopping the study if they conclude that excessive adverse effects clearly linked to one of the treatment arms are occurring. The board will compile a report for each meeting and present their findings to the PI.

To date there have been no adverse events..

No studies have been conducted in the last year so no DSMB assessment of the study has been performed since the last submission of this protocol. We will submit data to the DSMB once new subjects have been recruited.

[Back to Top](#)

**Subject Complaints:** Describe procedures (other than information provided in consent document) for handling subject complaints or requests for information about the research. The procedures should offer a safe, confidential, and reliable channel for current, prospective, or past research subjects (or their designated representative) permitting them to discuss problems, concerns and

questions, or obtain information.

